Although nOPV2 was designed to be more genetically stable than mOPV2, there is a lack of real-world evidence on its recombination behaviours. Therefore, in the current study, we will assess recombinants at two timepoints for all arms (8 and 10 weeks; two and four weeks post-vaccination, respectively). Timepoints for stool collection were selected based on when shedding would be expected to be high in children without pre-existing mucosal immunity.

While phase I and II trials have measured shedding post-vaccination among nOPV2 vaccine recipients, these were among individuals with previous poliovirus vaccination [14, 16]. There is also currently a lack of data to estimate potential secondary transmission of the vaccine virus to close contacts of vaccine recipients. The household transmission component of the study will be descriptive of not include a Sabin 2 comparison group; nevertheless, it is important to assess the transmissibility of nOPV2 in order to better anticipate risks.

Overall, these data will be programmatically valuable and can inform future decision making around nOPV2 use, particularly for outbreak response.

Research Design and Methods

Study Area

Mirpur is one of the 14 Thanas of Dhaka city with a population of about two million in an area of 59 square kilometers. Mirpur Thana of Dhaka city is divided into 14 sections. The area is densely populated and is about eight kilometers from icddr,b's Dhaka Hospital. The population is stable with low socioeconomic conditions. The average income in the slum areas of Mirpur is Tk.4200 (about US \$55) per month per family. Only 25% of fathers and 15% of mothers have more than five years of formal education. The study will be conducted in sections 1- 2, 6-7 and 10-13 of Mirpur, which has a population of about 500,000. icddr,b and CDC have collaborated on multiple polio vaccine trials that were conducted in the study clinic in Mirpur [23, 24].

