2. A diagnosis or suspicion of immunodeficiency disorder either in the infant or in an immediate family member.
3. A diagnosis or suspicion of bleeding disorder that would contraindicate administration of bOPV or nOPV2 or collection of blood by venipuncture.
4. Acute diarrhoea, infection or illness at the time of enrolment (6 weeks of age) that would require infant's admission to a hospital.
5. Acute vomiting and intolerance to liquids within 24 hours before the enrolment visit (6 weeks of age).
6. Evidence of a chronic medical condition identified by a study medical officer during physical exam.
7. Receipt of any polio vaccine (OPV or IPV) before enrolment based upon documentation or parental recall.
8. Known allergy/sensitivity or reaction to polio vaccine, or its contents.
9. Infants from multiple births. Infants from multiple births will be excluded because the infant(s) who is/are not enrolled would likely receive OPV through routine immunization and transmit vaccine poliovirus to the enrolled infant. Even if all births from a multiple birth could be enrolled in the study, we will exclude multiple births as discontinuation of one may lead to discontinuation of multiple vaccine recipients.
10. Infants from premature births (<37 weeks of gestation).

Sibling

1. Participant in a previous poliovirus vaccine clinical trial.
2. Unable to participate in the study until and including the Clinic Visit at 10 weeks (age of vaccine recipient).
3. A diagnosis or suspicion of immunodeficiency disorder either in the sibling or in an immediate family member.
4. Acute diarrhoea, infection or illness at the time of enrolment that would require sibling's admission to a hospital.
5. Evidence of a chronic medical condition identified by a study medical officer during physical exam.

Discontinuation Criteria

Vaccine Recipient

1. Withdrawal of consent for participation for any reason.
2. Request by parents of vaccine recipient to terminate all study procedures.
3. Identification of immunodeficiency disorder, bleeding disorder or another medical condition for which continued participation, in the opinion of the principal investigator, would pose a risk to the vaccine recipient to continue in the study.
4. Receipt of immunosuppressive medications.

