5. Receipt of any polio (OPV or IPV) vaccine outside of study after enrolment (as per parent's report). Vaccine recipients who received polio vaccines outside of the study, including any polio vaccine administered in polio campaigns, would be excluded from further study procedures.
6. Temporary discontinuation may occur when there has been a temporary suspension of study activities. Study enrolment will be suspended from 12 weeks before the start of polio campaigns in the study areas to 6 weeks after the completion of polio campaigns in the study areas. This measure is to prevent potential interference from polio vaccine administered during polio campaigns in the study areas. If vaccine recipients receive vaccine during polio campaigns, they would be discontinued from further study procedures.

7. Unable to collect or obtain blood at enrolment (Clinic Visit at 6 Weeks of Age).
8. Allergic reaction to a prior dose of polio vaccine, or its contents.
9. Premature termination of the study.

Sibling

1. Vaccine recipient is discontinued from the study.
2. Withdrawal of consent for participation for any reason.
3. Receipt of any polio (OPV or IPV) vaccine after enrolment (as per parent's report). Siblings who receive polio vaccines during their participation in the study, including any polio vaccine administered in polio campaigns, would be excluded from further study procedures.

Description of Study Vaccines

Two polio vaccines will be used in the study: bOPV and nOPV2

1. Bivalent oral polio vaccine (bOPV)

- a. Manufacturer: Bio Farma
- b. Presentation: the vaccine will be available in multi-dose vials
- c. Formulation: Each dose (2 drops = 0.1 ml).
- d. Administration: one vaccine vial will be used per participant.
- e. Previous use at icddr,b: bOPV is part of the routine immunization schedule in Bangladesh.

2. Candidate 1 novel monovalent oral poliovirus vaccine type 2 (nOPV2)

- a. Manufacturer: Bio Farma

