Field workers will inform parents about the study and briefly explain the study procedures, including stool sampling from both the vaccine recipient and the sibling. If interested in participating, parents will be asked to visit the study clinic when the vaccine recipient is 6 weeks of age to obtain comprehensive information on the study and to complete enrolment procedures; both the vaccine recipient and sibling will need to be present at this visit. Parents will be provided transport costs for all study visits to/from the clinic.

The below description summarizes the study clinic and home visits over the course of the study. Vaccine recipients may additionally visit the study clinic for routine childhood vaccinations or for management of adverse events. Although non-study vaccines included in the routine immunization schedule in Bangladesh will be available and vaccination will be encouraged, parents will have the final decision to vaccinate their infant. Injectable non-polio, routine immunization vaccines will be administered at the recommended body site per the national guidelines of Government of Bangladesh. If a study visit involves collection of blood as well as administration of study vaccines, then blood collection will precede study vaccine administration. For Arm B, concomitant administration will be defined as nOPV2 provided first, followed by bOPV on the same day in rapid succession with a target of ≤ 5 minutes apart.

Enrolment visit – 6 weeks of age (acceptable range 42–48 days) [All arms; sibling must also be present at this clinic visit, but not subsequent clinic visits]

During this visit, the following procedures will be conducted:

1. The medical officer will confirm that the vaccine recipient and sibling are eligible to participate. If the vaccine recipient and sibling are eligible, all study procedures will be explained to the parents. The parents will be requested to provide informed consent; consent will be documented per study procedures.
2. The vaccine recipient will be assigned a participant identification number (PID) and to a study arm according to a pre-determined randomization scheme. Further details of the randomization scheme are described in the “Data Analysis” section.
3. Vaccination record of the sibling will be obtained and recorded by the medical officer.
4. Socio-demographic and clinical information will be recorded on the corresponding electronic case report form (eCRF).

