Vaccine recipients will be enrolled at 6 weeks of age. Enrolment at this early age is required because the study is assessing the immunogenicity of poliovirus vaccines that are routinely administered at this age. The current schedule for polio immunization in Bangladesh includes three doses of bOPV administered at 6, 10 and 14 weeks of age plus two fractional IPV (fIPV) ID doses administered at 6 and 14 weeks of age. Delaying vaccine recipient enrolment until they are older will not allow assessing the immunogenicity of alternative polio vaccines and vaccination schedules because most vaccine recipients will be immune as a result of the polio vaccines they received through routine immunization.

Potential Benefits and Compensation to Vaccine recipients

Vaccine recipients will receive all non-polio routine immunizations (BCG, Penta, PCV) as per the routine immunization schedule of Bangladesh. After completion of study activities, vaccine recipients in Arms A and B will receive three doses of bOPV. The three doses of bOPV will be given in 4-week intervals

beginning at 18 weeks of age. All vaccine recipients will also receive two doses of fIPV. The routine polio immunization schedule in Bangladesh is three doses of bOPV along with two doses of fIPV. During study visits, vaccine recipients will be examined by medical officers and their growth and development will be assessed. In addition, vaccine recipients and siblings will be offered advice on diagnosis and treatment of any other illnesses they experience during the study period at no cost.

For the larger public health community, the results of this clinical trial may be used to inform outbreak response vaccination strategies.

Risks to Vaccine recipients and Siblings

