- *Child is ELIGIBLE if all answers to questions 1-4 are YES. If the child is eligible, explain what the child's participation in the study will involve and provide the information sheet.*
- *Child is NOT ELIGIBLE if any of the answers to questions 1-4 is NO. If the child is NOT eligible, STOP. The sibling and vaccine recipient are not eligible to continue with study enrollment. Enrollment cannot continue for the vaccine recipient unless an eligible sibling is brought to the clinic to be enrolled on the same day.*

Do the parents give consent for their child to participate in the study? Yes / No

- *If parents DO NOT consent, ask them the following. When finished, thank them for their time and STOP.*

Why are you not interested in having your child participate in the study? (Circle all that apply) Study purpose unclear

Busy-No time / Other (specify): _____

- *If parents DO consent, continue with the study procedures.*

Polio vaccination history:

1. Is the vaccination card present? Yes / No

Note: If present, answer questions below based on the vaccination card.

2. Has the child ever received bOPV? Yes / No

2a. If yes, how many doses of bOPV? _____

2b. Date of most recent bOPV vaccination (dd/MMM/yy): / /

Clinic Visit at 6 weeks of Age – Sibling

3. Has the child ever received tOPV? Yes / No

3a. If yes, how many doses of tOPV? _____

3b. Date of most recent tOPV vaccination (dd/MMM/yy): / /

4. Has the child ever received fIPV? Yes / No

4a. If yes, how many doses of fIPV? _____

4b. Date of most recent fIPV vaccination (dd/MMM/yy): / /

5. Has the child ever received IPV? Yes / No

5a. If yes, how many doses of IPV? _____

5b. Date of most recent IPV vaccination (dd/MMM/yy): / /

Name and signature of medical officer: _____

Phone Call or Home Visit 24–48 hours after 6-week vaccination***To be completed for vaccine recipients in all Arms***Date of call/visit (dd/MMM/yy): / / Time of call/visit (hh:mm): **Adverse events**

Since the vaccine recipient was at the clinic for the “Clinic Visit at 6 weeks”, have they had any of the following symptoms?

1. Fever: No Yes If yes, please describe _____

If yes, and thermometer available: Grade 1: 37.5° C- 38.0 ° C Grade 2: 38.1° C- 39.0 ° C
 Grade 3: >39.0 ° C

2. Vomiting: No Yes If yes, Grade 1: 1 episode/24 hours Grade 2: 2-5 episodes/24 hours

Grade 3: ≥ 6 episodes/24 hours

3. Abnormal crying: No Yes If yes, Grade 1: < 1hour Grade 2: 1-3 hours

Grade 3: >3 hours

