1. Were there any problems in giving the two stool kits to the parents? Yes / No

1a. If yes, explain _____

Name and signature of study staff: _____

Home Visit #2: To be completed on the day the stool samples are picked up.**For study vaccine recipient:**

1. Stool sample collected? Yes / No 1a. If no stool obtained, why not? _____

2. Date of stool collection (dd/mm/yyyy): / /

3. Time of collection (hh:mm): :

4. Sufficient quantity (8 grams)? Yes / No 4a. If insufficient, specify reasons: _____

For sibling of study vaccine recipient:

5. Stool sample collected? Yes / No 5a. If no stool obtained, why not? _____

6. Date of stool collection (dd/mm/yyyy): / /

7. Time of collection (hh:mm): :

8. Sufficient quantity (8 grams)? Yes / No 8a. If insufficient, specify reasons: _____

Name and signature of study staff: _____

Data Entry: To be completed when data entered into RedCapDate of data entry in RedCap (dd/mm/yyyy): / /

Name and signature of person entering data: _____

Household Visit at 10 weeks of Age*To be completed for vaccine recipients in all Arms***Home Visit #1: To be completed on the day the stool kits are delivered to the parents.****Date stool kits delivered** (dd/mm/yy): / /

1. Were there any problems in giving the two stool kits to the parents? Yes / No

1a. If yes, explain _____

Name and signature of study staff: _____

Home Visit #2: To be completed on the day the stool samples are picked up.**For study vaccine recipient:**

1. Stool sample collected? Yes / No 1a. If no stool obtained, why not? _____

2. Date of stool collection (dd/mm/yyyy): / /

3. Time of collection (hh:mm): :

4. Sufficient quantity (8 grams)? Yes / No 4a. If insufficient, specify reasons: _____

For sibling of study vaccine recipient:

5. Stool sample collected? Yes / No 5a. If no stool obtained, why not? _____

6. Date of stool collection (dd/mm/yyyy): / /

7. Time of collection (hh:mm): :

8. Sufficient quantity (8 grams)? Yes / No 8a. If insufficient, specify reasons: _____

Name and signature of study staff: _____

Data Entry: To be completed when data entered into RedCapDate of data entry in RedCap (dd/mm/yyyy): / /

Name and signature of person entering data: _____

Clinic Visit at 10 weeks of AgeDate of visit (dd/mm/yy): / / **Clinical History**

1. Is the child currently breastfed? No breastfeeding / Partial breastfeeding / Exclusive breastfeeding
2. Has the child received any vaccine since last visit? Yes / No 2a. If yes, specify: _____

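### After enrolment, outside polio vaccination in the infant is identified by parent's report alone; a card check at follow-up would be a cheap, minor improvement

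*Protocol*

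**What the plan says.** Under Discontinuation Criteria, Vaccine Recipient, item 5 is "Receipt of any polio (OPV or IPV) vaccine outside of study after enrolment (as per parent's report". The sibling rule uses the same source: "Receipt of any polio (OPV or IPV) vaccine after enrolment (as per parent's report". The Concomitant Medications and Vaccines section also discontinues an infant who has an outside polio dose, but names no source of information.

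Before enrolment, the infant exclusion is "Receipt of any polio vaccine (OPV or IPV) before enrolment based upon documentation or parental recall", so recall alone is enough there too.

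In Appendix A, the infant's 10-, 14- and 18-week clinic forms ask "Has the child received any vaccine since last visit", with space to specify and to give a date. They have no card field and no infant question naming polio vaccine. For the sibling, the Screening Form has the mother bring vaccination records to the 6-week visit. The sibling's 6-week form says "Note: If present, answer questions below based on the vaccination card". The 10-week form then asks specifically whether the sibling has had a poliovirus vaccine.

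The serology sets are defined under Data Analysis. Intention-to-treat requires consent not withdrawn and adequate blood at enrolment and at the endpoint visit. Per-protocol adds timing conditions on blood and on the scheduled study vaccines. Neither has a condition on outside polio vaccine.

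**The concern.** The infant carries the primary endpoint, yet an outside dose in the infant is sought less carefully than one in the sibling, who serves descriptive objectives only. The protocol evidently regards bringing a record to the clinic as practicable.

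Exposure is plausible. The national schedule, as described in the ethics section, has bOPV at 6, 10 and 14 weeks and "two fractional IPV (fIPV) ID doses administered at 6 and 14 weeks of age". Study infants receive no fIPV until 18 weeks, and Arm A receives no bOPV until then. Parents know the arm. A reported outside dose ends participation, which may discourage reporting. For Mirpur, the Study Area section says "Only 25% of fathers and 15% of mothers have more than five years of formal education", so recall of which vaccine was given may be imperfect.

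A missed outside dose that produces a response in either arm tends to pull the arms together. In a non-inferiority comparison that is the anti-conservative direction, and a per-protocol set that depends on the same report cannot correct it.

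**Working it through.** **The plan's own figure first.** Inputs from Sample Size Calculation: 85% response in both arms (types 1 and 3), margin 10 points, 90% power, α 0.05 (sidedness not stated). With unpooled variance and one-sided α 0.05:

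- n = 2 × 0.85 × 0.15 × (1.645 + 1.282)² / 0.10² = 218.4, or 219 per arm.
- With continuity correction, n/4 × (1 + √(1 + 4/(n × 0.10)))² = 237.96, or 238 per arm.
- Attrition: 238 / 0.9 = 264.4, or 265.

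Both stated figures reproduce. They do not depend on how outside vaccination is found.

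**Sensitivity to missed outside doses.** The documents give no rate, so the following are assumptions. True responses are 85% (Arm C) and 75% (Arm B), exactly at the margin, with n = 238 per arm. A share u of each arm has an undetected outside dose before the endpoint blood and responds at q, the same in both arms.

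- pC = 0.85(1 − u) + qu and pB = 0.75(1 − u) + qu, so the difference is 0.10(1 − u) whatever q is.
- SE = √[pC(1 − pC)/238 + pB(1 − pB)/238].
- Chance of concluding non-inferiority = Φ((0.10 − difference)/SE − z), with z = 1.645 for one-sided 0.05 or 1.960 for one-sided 0.025.

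Example, u = 5% and q = 100%: pC = 0.8575, pB = 0.7625, difference 0.095, SE = 0.0357; 0.005/0.0357 − 1.645 = −1.505; Φ = 0.066.

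| u | Observed gap (points) | From one-sided 5% | From one-sided 2.5% |
|---|---|---|---|
| 0 | 10.0 | 5.0% | 2.5% |
| 1% | 9.9 | 5.3% | 2.7% |
| 2% | 9.8 | 5.6% | 2.8% |
| 5% | 9.5 | 6.6% | 3.4% |
| 10% | 9.0 | 8.7% | 4.7% |

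These rows use q = 100%. With q = 95% the results are almost the same (6.6% and 8.7% at u = 5% and 10%, from one-sided 5%).

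**If affected infants still differ by arm.** Suppose they respond at 95% in Arm C and 90% in Arm B. At u = 5% the gap is 0.10 × 0.95 + 0.05 × 0.05 = 0.0975 and the error is 5.8%. At u = 10% the gap is 0.10 × 0.90 + 0.05 × 0.10 = 0.095 and the error is 6.6%. If the full 10-point gap persists among them, the error stays at 5.0%.

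**Which doses can matter.** Outside bOPV carries types 1 and 3 only, so this mechanism applies to C versus B. Outside fIPV carries all three types. Only doses before the endpoint blood count. The primary blood is drawn at 14 weeks, before any vaccine given at that visit, so a routine 14-week dose given on or after the draw cannot affect the primary endpoint, though it can affect the 18-week secondary one.

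**The case against.** Much of the opposing case stands.

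- A reader might infer that the protocol demands documents before enrolment and drops them afterwards. It does not: the pre-enrolment infant rule accepts recall alone, the infant's 6-week form is a bare yes/no, and the sibling's card is used at baseline only, if present. After enrolment the sibling rule also rests on parent's report. The contrast that remains is in the forms.
- The follow-up forms do ask parents to specify the vaccine and date. They also record the Penta and PCV dose number given, or the reason for not giving it, which may reveal an outside session. The unqualified wording under Concomitant Medications and Vaccines leaves staff free to act on a card if they see one.
- Exposure is limited by design. Enrolment is suspended around campaigns, and routine vaccines are given at study visits with the polio component replaced. The statement that "parents will have the final decision to vaccinate their infant" concerns accepting non-study vaccines and is no evidence that families go elsewhere. These measures reduce outside doses but do not detect them.
- A reader might infer that infants with known outside doses are analysed per protocol. Generally they are not: a dose known before the endpoint visit stops further procedures, so there is no endpoint blood. The gap concerns doses never reported, or discovered only after that blood was drawn.
- Finer per-protocol exclusions may sit in a statistical analysis plan, and card checks in the planned SOPs; neither is shown. That is why this is a suggestion about the source and forms the protocol does fix, not a charge of omission.

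**Conclusion.** A minor weakness in ascertainment that is worth repairing because the repair is cheap. The discontinuation rule names one unverified source for the infant, the infant's follow-up forms prompt neither a card check nor a polio question, and a missed dose before the endpoint blood remains in both serology sets.

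The effect is conditional and probably modest: about 0.3 to 0.6 percentage points of added one-sided error at 1–2% contamination, 1.6 at 5% and 3.7 at 10%. This assumes a true deficit exactly at the margin and near-equal response among affected infants in both arms; if the arms still differ among them, the effect is smaller or absent. It would be wrong to read this as showing that the trial's non-inferiority conclusion is biased. The documents give no rate of outside vaccination, no stated figure is wrong, and the sample size is unaffected.

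**What to change.** - In item 5 of the vaccine recipient discontinuation criteria, change the source to the infant's vaccination card where available, plus parent's report. This alters how an outside dose is found, not what follows from it.
- Ask parents to bring the infant's card to the 10-, 14- and 18-week visits.
- Add one line to each of those forms: *Card seen? Any OPV, IPV or fIPV since last visit? Date.*
- Add to the per-protocol serology sets: no documented or reported outside polio dose before the endpoint blood, including a dose discovered at a later visit.

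The cost is one line on three forms, a reminder to parents, and possibly a few more per-protocol exclusions. The figures of 238 and 265 per arm do not change.
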